#### 18.6. PHYSICAL EXAMINATION

The following summaries will be provided for physical examination data for combination therapy by visit on SAF:

- Summary of Physical examination
- Shift from baseline according to the physical examination findings.

#### 18.7. OTHER SAFETY ASSESSMENTS

No other safety assessment will be collected for this study.

# 19. DATA NOT SUMMARIZED OR PRESENTED

The other variables and/or domains not summarized or presented are:

- Comments
- Contacts
- These domains and/or variables will not be summarized or presented, but will be available in the clinical study database, SDTM and/or ADaM datasets.

Document: \\ieedc-vnasc01\BIOSdata\Menarini\NebZof\KZA41200\Biostatistics\Documentation\SAP

Author: [name] Version Number: Final V1.0

Version Date: [14Dec2021]

Template No.: CS\_TP\_BS016 Revision 6 Reference: CS\_WI\_BS005

Page 32 of 37

### APPENDIX 1. PROGRAMMING CONVENTIONS FOR OUTPUTS

### **IQVIA OUTPUT CONVENTIONS**

Outputs will be presented according to the following Global Bios > Processes > GBIOS Processes - Implementation Guidelines and Templates > General Guidelines and Templates > Output Conventions.

#### **DATES & TIMES**

Depending on data available, dates and times will take the form yyyy-mm-ddThh:mm:ss.

#### **SPELLING FORMAT**

English US

#### PRESENTATION OF TREATMENT GROUPS

For outputs, treatment groups will be represented as follows and in the given order:

Therapy	Treatment Group	For Tables and Graphs	For Listings (include if different to tables)
Monotherapy	NEB 5mg	NEB 5mg	NEB 5mg
Monotherapy	ZOF 30mg	ZOF 30mg	ZOF 30mg
Combination therapy	NEB+ZOF	NEB+ZOF	NEB+ZOF

Document: \\ieedc-vnasc01\BIOSdata\Menarini\NebZof\KZA41200\Biostatistics\Documentation\SAP

Author: [name] Version Number: Final V1.0

Version Date: [14Dec2021]

Template No.: CS\_TP\_BS016 Revision 6 Reference: CS\_WI\_BS005

Effective Date: 02Dec2019

Page 34 of 37

#### PRESENTATION OF VISITS

Visit 1 Week -4

Visit 2 Week 0

Visit 3 Week 8

For outputs, visits will be represented as follows and in that order:

Long Name (default)	Short Name
Screening (Visit 1)	Scr (V1)
Baseline (Week 0) or Week 0 (Visit 2)	BL(W0) or W0(V2)
Week 8 (Visit 3)	W4 (V3)

#### LISTINGS

All listings will be ordered by the following (unless otherwise indicated in the template):

- Treatment group (Monotherapy and Combination therapy)
- Center-patient ID,
- Date (where applicable)

Document: \\ieedc-vnasc01\BIOSdata\Menarini\NebZof\KZA41200\Biostatistics\Documentation\SAP

Author: [name] Version Number: Final V1.0

Version Date: [14Dec2021]

Template No.: CS\_TP\_BS016 Revision 6 Reference: CS\_WI\_BS005

Page 35 of 37

# APPENDIX 2. PARTIAL DATE CONVENTIONS

Imputed dates will NOT be presented in the listings.

#### ALGORITHM FOR TREATMENT EMERGENCE OF ADVERSE EVENTS:

START DATE	STOP DATE	ACTION
Known	Known/Partial/ Missing	If start date < study med start date, then not TEAE  If start date >= study med start date, then TEAE
Partial, but known components show that it cannot be on or after study med start date	Known/Partial/ Missing	Not TEAE
Partial, could be on or after study med start date OR Missing	Known	If stop date < study med start date, then not TEAE  If stop date >= study med start date, then TEAE
	Partial	Impute stop date as latest possible date (i.e. last day of month if day unknown or 31st December if day and month are unknown), then:  If stop date < study med start date, then not TEAE  If stop date >= study med start date, then TEAE
	Missing	Assumed TEAE

Document: \\ieedc-vnasc01\BIOSdata\Menarini\NebZof\KZA41200\Biostatistics\Documentation\SAP

Author: [name] Version Number: Final V1.0

Version Date: [14Dec2021]

Template No.: CS\_TP\_BS016 Revision 6 Reference: CS\_WI\_BS005

Effective Date: 02Dec2019

Page 36 of 37

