#### 10.2.1 Physical Examination:

Physical examination will be performed according to the local practice. Physical examination will consist of the following body systems: eyes, ears, nose, throat, cardiovascular system, respiratory system, gastrointestinal system, dermatologic system, extremities, musculoskeletal system, nervous system, and lymph nodes. Height and weight will also be recorded at Screening. Any new finding, or worsening of a previous finding, should be reported as a new AE.

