#### 14.5.7 Safety Analysis

#### **Adverse Events:**

Adverse events recorded during the study will be mapped to a system organ class (SOC) and preferred term (PT) using the current Medical Dictionary for Regulatory Activities (MedDRA). Treatment-emergent adverse events are defined as new AEs that occur on or after the date/time of the first administration of study medication or worsen if an AE started prior to the start of first administration of study medication.

All the AEs will be presented with the following:

- Number of cases
- Number of patients with AE
- Percentage of patients with AE

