#### 18.1. ADVERSE EVENTS

Adverse Events (AEs) will be coded using Medical Dictionary for Regulatory Activities (MedDRA) central coding dictionary, Version 23.1.

Treatment emergent adverse events (TEAEs) are defined as AEs that started or worsened in severity on or after the first dose of study medication (Combination therapy).

See Appendix 2 for handling of partial dates for AEs. In the case where it is not possible to define an AE as treatment emergent or not, the AE will be classified by the worst case; i.e. treatment emergent.

An overall summary of number of patients within each of the categories described in the sub-section below, will be provided as specified in the templates. Listings will include TEAEs and Non-TEAEs.

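### SAP Appendix 2 classes any adverse event known to have started before the combination as not treatment-emergent, with no test for worsening, which contradicts the definition in SAP 18.1

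*SAP*

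**What the plan says.** SAP 18.1 defines TEAEs as "AEs that started or worsened in severity on or after the first dose of study medication" and states in parentheses that the study medication meant is the combination therapy. Protocol 14.5.7 also includes worsening: beyond new events it counts those that "worsen if an AE started prior to the start of first administration of study medication". The protocol sentence does not name the combination; only the SAP does.

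SAP Appendix 2 turns this into an algorithm based on start and stop dates:

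- Start date known: "If start date < study med start date, then not TEAE"; on or after that date, TEAE.
- "Partial, but known components show that it cannot be on or after study med start date": not TEAE, whatever the stop date.
- "Partial, could be on or after study med start date OR Missing": TEAE if the stop date (imputed as late as possible when partial) is on or after the start of study medication, or if the stop date is missing.

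SAP 6.1 sets the reference start date at the first combination dose at Visit 2, so an event that began in the run-in lies before it. SAP 18.1.1 to 18.1.4 restrict the tables for incidence (with severity and relationship), discontinuation, serious events and fatal events to TEAEs. SAP 18.1 keeps non-TEAEs in the listings.

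On recording, Protocol 10.2.1 says of physical examination: "Any new finding, or worsening of a previous finding, should be reported as a new AE". Protocol 11.9 makes a laboratory abnormality an adverse event when it is new or has worsened and the investigator considers it clinically relevant.

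**The concern.** Every patient who receives the combination has first spent about four weeks on one of its two components. Patients who do not tolerate the monotherapy leave at Visit 2, but a patient with a tolerable ongoing event continues. If that event becomes more severe once the second drug is added, it bears directly on the secondary objective of combination safety and tolerability in SAP 2.2, and SAP 18.1 plainly means to count it. The algorithm that a programmer would apply to the same record excludes it.

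The result also runs against the SAP's own cautious approach. Under 18.1, an event whose status cannot be determined is treated as treatment-emergent, and Appendix 2 assumes TEAE when both dates are missing. A documented worsening on the combination would therefore be left out of the tables, while an event with no dates at all would be included.

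**Working it through.** The plan gives no figure to reproduce. The check applies the definition in SAP 18.1 and the algorithm in Appendix 2 to the same events and compares the classifications.

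Inputs: the definition from SAP 18.1; the rows of the Appendix 2 algorithm; the first combination dose as the cut-off, from SAP 6.1 and 18.1. The dates are illustrative assumptions: combination start 15 March 2021, run-in onset 1 March 2021, worsening 10 April 2021 and, where a stop date is known, 30 April 2021.

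Rules:

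- Definition: TEAE if start ≥ first combination dose, or severity increased on or after first combination dose.
- Algorithm: TEAE if the known start ≥ first combination dose. If the start is partial but certainly earlier, not TEAE. If the start is ambiguous or missing, TEAE when the stop (imputed late if partial) ≥ first combination dose or the stop is missing.

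| Event | Appendix 2 | SAP 18.1 |
|---|---|---|
| 1. Known start 1 March, worsens 10 April, ongoing | not TEAE | TEAE |
| 2. Known start 1 March, worsens 10 April, stops 30 April | not TEAE | TEAE |
| 3. Partial start February 2021, worsens 10 April | not TEAE | TEAE |
| 4. Partial start March 2021 (ambiguous), worsens 10 April, ongoing | TEAE | TEAE |
| 5. Known start 1 March, no worsening, stops 30 April | not TEAE | not TEAE |
| 6. Worsening entered as a new record starting 10 April | TEAE | TEAE |

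The rules disagree in rows 1 to 3: a start known to precede the combination, a later worsening, and a single record. Row 4 agrees only because an ambiguous date defaults to TEAE, not because worsening was tested. Row 6 agrees because the new record carries its own start date.

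Next, which worsenings reach row 6? Protocol 10.2.1 sends worsened examination findings there. Protocol 11.9 makes clinically relevant laboratory worsening a reportable event, which passes if entered with its own start date. Neither document has such a rule for a symptom that began in the run-in, so symptoms kept on one record stay in rows 1 to 3.

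Finally, which outputs depend on the flag? The tables in SAP 18.1.1 to 18.1.4 do. The following do not: the listings (18.1), disposition (9.1), deaths (18.2), laboratory data (18.3), ECG (18.4), vital signs (18.5) and physical examination (18.6).

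**The case against.** The strongest reply is that SAP 18.1 holds the definition and refers to Appendix 2 only for partial dates, so a programmer who follows 18.1 could still flag worsening. This stands in part: the documents show an inconsistency, not what will be programmed. It does not remove the problem, because the first row of the algorithm governs fully known start dates and the table is headed as the algorithm for treatment emergence.

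A second reply is that worsening becomes a new record anyway. That stands for examination findings and may stand for clinically relevant laboratory changes. Neither document states it for other events.

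A reader might also infer more than the documents support:

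- That every event starting before the combination is excluded. Only events known to have started earlier are; ambiguous or missing start dates are TEAE unless the stop date is earlier.
- That these events vanish from the safety output. They leave only the TEAE-based tables.
- That Protocol 14.5.7 directly contradicts Appendix 2 on the combination dose. It refers to study medication without naming the combination. The direct contradiction lies within the SAP, between 18.1 and Appendix 2.
- That the loss can be sized. Assuming 10% of 216 patients carry an event forward and 20% of those worsen gives 216 × 0.10 × 0.20 = 4.3 patients; assuming 20% and 30% gives 216 × 0.20 × 0.30 = 13.0. None of these rates comes from the documents, and withdrawal at Visit 2 for intolerance makes the pool smaller by an unknown amount.

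**Conclusion.** The contradiction is real, and it is confined to the SAP's adverse event classification. If Appendix 2 is programmed as written, a run-in event with a start date known to be earlier, which worsens on the combination and remains on one record, is a TEAE under 18.1 but not under the algorithm. It is then missing from the TEAE-based incidence, severity, relationship, discontinuation, serious and fatal-event tables. The events at risk are mainly symptoms.

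The size of the loss is unknown. The direction is not: for these events the tables can only understate what 18.1 asks for. The primary endpoint is not affected.

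The conclusion assumes that the study medication start date in Appendix 2 means the first combination dose, as SAP 6.1 and 18.1 indicate, and that no unseen eCRF guidance already requires a new record for every worsening. If such guidance exists, the gap closes in practice, and SAP 18.1 and Appendix 2 need only cite it.

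**What to change.** Make Appendix 2 agree with 18.1. To both rows that end in not TEAE, add: *unless severity increased on or after the first combination dose, in which case TEAE, tabulated at the post-dose severity*.

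This needs a dated severity change on a single record, and nothing in the documents shows that the eCRF holds one. If it does not, state instead in the eCRF completion guidance and in SAP 18.1 that any worsening of an ongoing event is entered as a new record with its own start date. The present algorithm then classifies it correctly.

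Choose one route. With both in place, one worsening could be flagged on two records and inflate the number of cases that Protocol 14.5.7 asks for.

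The cost is one SAP edit before database lock, which Protocol 14.7 allows for, with minor programming; or, on the other route, a line of eCRF guidance and a matching sentence in SAP 18.1. Changing the text of Protocol 11.9 is not necessary and would require an amendment under Protocol 14.6.

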#### **Protocol Template**

Sponsor: Menarini Pharmaceutical Study Code: MEIN/19/ZoNe-HYP/001

Protocol Version 1 of 16/07/2020

After the run-in period, the patients will be treated with the extemporaneous combination of NEB 5 mg and ZOF 30 mg for 8 weeks (assessment period), ie, from Week 0 (Visit 2) till Week 8 (Visit 3).

To correctly evaluate the additional effect of the combination therapy, the number of patients with uncontrolled BP on NEB or ZOF monotherapy needs to be balanced at Visit 2. In order to maintain a 1:1 ratio during the assessment period, a cap of 110 patients for each arm (ie, NEB and ZOF) will be included at Visit 2 in order to maintain a balanced number of uncontrolled patients entering the assessment period for each drug. The evaluation will be done every 50 patients. If the rate of entrance in the assessment period for one of the 2 tested drugs will deviate more than 5%, a corrective measure will be initiated: according to the enrolment site statistics, one or more sites will be informed to enrol a greater number of patients being treated with the least represented drug in the assessment period. A total number of 290 patients will be screened considering 25% of drop-out rate, to obtain approximately 216 completed patients at the end of the study.

Blood pressure and heart rate will be measured at all visits using a calibrated, fully automated machine with a cuff that is appropriate to the size of the upper arm. If a fully automated machine is not available, BP may be measured manually. The same method (either automated or manual) and the same arm (right or left) must be used throughout the study. The patient should be in a seated position with feet touching the floor. Patients should be seated quietly for several minutes in a chair with their backs supported, their feet flat on the ground, and their arms bared and supported at heart level. At each clinic visit, 3 BP measurements will be collected 24 hours (±3 hours) after the last study drug intake and the mean values will be recorded. Each BP measure must be recorded within ±2 mmHg. Patients will be instructed to take study medication at the same time each day except on the days of study visits when study medication will be taken after all visit evaluations have been performed.

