#### BP measurements:

Blood pressure will be measured at all visits. The arm with the higher mean DBP will be identified at Screening and will be used in all subsequent visits for BP monitoring. Blood pressure measurements should be performed as nearly as possible at the same time of the day (between 7:00 AM to 12:00 noon), on the same arm, by the same personnel, and using the same calibrated equipment at each visit.

All BP measurements will be performed after at least 10 minutes of rest; in sitting position in triplicate (spaced by at least 1 minute), and once in standing position using a calibrated and validated automated sphygmomanometer. The mean of the 3 recordings in the sitting position will be used as the BP value for that visit and recorded in the source document and in the eCRF. All BP measurements during the treatment period will be performed as through readings (ie, 24+3 hours after the last study treatment intake). For this purpose, patients will be instructed to take study treatment at the same time each day except on the days of study visits when study treatment will be taken after all visit evaluations have been performed.

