### 6. GENERAL CONSIDERATIONS

### **6.1.** REFERENCE START DATE AND STUDY DAY

Study Day will be calculated from the reference start date and will be used to show start/stop day of assessments and events. Reference start date is defined as the day of the first dose of study drug (combination therapy) (Visit 2), (Day 1 is the day of the first dose of study drug ) and will appear in every listing where an assessment date or event date appears.

- If the date of the event is on or after the reference date, then:
- Study Day = (date of event reference date) + 1. If the date of the event is prior to the reference date, then: Study Day = (date of event – reference date).

In the situation where the event date is partial or missing, Study Day, and any corresponding durations will appear partial or missing in the listings.

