#### **6.2.** BASELINE

Unless otherwise specified, baseline is defined as the last non-missing measurement taken same day or prior to reference start date (including unscheduled assessments) before first dose of study medication (combination therapy). Adverse Events (AEs) and medications commencing on the reference start date/time will be considered post-baseline, unless the start time of the AE is known to be prior to the first dosing of the study drug. Since there is no Lab assessment in Visit 2, Lab values collected at Visit 1 will be considered baseline for Lab data.

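### SAP Appendix 2 flags adverse events on the first combination dose day by date alone, so an event known to precede that dose counts as a combination TEAE, contrary to SAP 18.1 and protocol 14.5.7

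*SAP*

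**What the plan says.** Four places bear on when an adverse event becomes treatment-emergent.

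- **SAP Appendix 2, algorithm for treatment emergence.** For a known start date the rule is "If start date >= study med start date, then TEAE". An earlier date is not a TEAE. Nothing is said about time of day or order relative to the dose.
- **SAP 18.1.** TEAEs are "AEs that started or worsened in severity on or after the first dose of study medication (Combination therapy"). The section refers to Appendix 2 for partial dates and treats an event as emergent when its status cannot be decided.
- **Protocol 14.5.7.** TEAEs are "new AEs that occur on or after the date/time of the first administration of study medication", or earlier events that worsen.
- **SAP 6.2.** Events beginning on the reference start date are post-baseline, "unless the start time of the AE is known to be prior to the first dosing of the study drug".

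The order of events at Visit 2 is also specified. SAP 6.1 states: "Reference start date is defined as the day of the first dose of study drug (combination therapy) (Visit 2"). Protocol 10.1 says that on visit days "study treatment will be taken after all visit evaluations have been performed"; protocol Section 7 and the footnote to Table 9.1 say the same. Protocol 7.1 places a physical examination, an ECG and an adverse event assessment at Visit 2. For the examination, protocol 10.2.1 says: "Any new finding, or worsening of a previous finding, should be reported as a new AE".

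**The concern.** A finding first made at the Visit 2 examination, with no earlier known onset, would naturally carry that day's date. At that moment the patient has taken only nebivolol or zofenopril alone. The Appendix 2 row compares the date with the date of the first combination dose, finds them equal, and flags the event as emergent on the combination.

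The same finding would also be used in two incompatible ways. Under SAP 6.2 the pre-dose Visit 2 assessment is baseline, and SAP 18.6 reports physical examination as shift from baseline. The finding would be baseline in the shift table and a combination TEAE in the adverse event table.

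Safety of the monotherapies and of the combination is a secondary objective (SAP 2.2), and the incidence tables in SAP 18.1.1 to 18.1.4 are built on the TEAE flag. A misclassified event goes straight into them. If its causality entry is missing, SAP 18.1.1.2 also counts it as probably related. Two programmers working from different sections could reach different TEAE counts.

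**Working it through.** The plan states no figure here, so the check sets the rules side by side. Take a first combination dose at 10:30 on the Visit 2 day (a time chosen only for illustration) and classify events around it:

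- by Appendix 2, comparing dates only;
- by the dose-based rule: SAP 18.1, protocol 14.5.7 with study medication read as the combination, and the SAP 6.2 exception, with worst case where the order is unknown.

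| Onset of event | Appendix 2 | Dose-based rule |
|---|---|---|
| Day before Visit 2 | not TEAE | not TEAE |
| Visit 2 day, known 08:30 (before dose) | **TEAE** | **not TEAE** |
| Visit 2 day, order unknown | TEAE | TEAE |
| Visit 2 day, known 14:00 (after dose) | TEAE | TEAE |
| Day after Visit 2 | TEAE | TEAE |

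One class conflicts: onset dated on the Visit 2 day and known to precede the dose.

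A finding made in the pre-dose assessments but recorded without a clock time needs a separate look. Its order is still known, because the protocol puts the assessments before the dose. On the definitions in SAP 18.1 and protocol 14.5.7 it is not emergent, and the worst-case rule should not be needed. Whether the SAP 6.2 exception reaches it is unclear, since that text asks for a known start time.

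On extent, the exposed window is one calendar day. Taking the period to end within the Visit 3 window of Day 53 to 59 (SAP Table A):

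- 1/53 = 1.9% of days
- 1/59 = 1.7% of days

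This is a share of days, not of events. The share of events could be larger because findings are recorded at visits, but the documents give no adverse event rate from which to estimate it.

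**The case against.** The best defence is that the plan read as a whole already gives the right answer. Both TEAE definitions run from the dose, SAP 6.2 has an exception for known earlier onset, and Appendix 2 is headed as a set of partial-date conventions, so its known-date row may be shorthand. Same-day events of unknown order are counted as emergent by a disclosed, conservative choice that errs against the combination. Listings show study day, so Day 1 events can be found.

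Much of this stands, and it limits the point. Several stronger readings are tempting but unsupported:

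- *Every event dated on the Visit 2 day is wrongly charged to the combination.* Only events known to be pre-dose conflict. Protocol 11.9 has events collected since consent, so a run-in symptom reported at Visit 2 with its earlier onset date is not a TEAE. No laboratory tests are done at Visit 2, and patients who do not tolerate monotherapy never receive the combination.
- *SAP 6.2 says the opposite of Appendix 2.* It shares the same-day default and departs from it only when the start time is known to be earlier.
- *Monotherapy events are under-counted in a comparison.* The SAP text specifies no incidence table for run-in events; non-TEAEs appear in listings, and SAP 18 plans no statistical comparison of safety between treatment groups.
- *The effect can be sized.* Assuming 2% to 5% of 216 patients affected gives 4.3 to 10.8 patients, and against an assumed 10% incidence (21.6 patients) an excess of 20% to 50%. Both rates are assumptions, so the result says nothing about this trial.

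The defence does not remove the conflict. The row covers known dates explicitly, under a title about treatment emergence. SAP 6.2 speaks of post-baseline status, does not name the TEAE flag, and is not cited in Appendix 2.

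**Conclusion.** The point holds for one class of event. The known-date row of Appendix 2 contradicts the plan's own TEAE definitions and omits the SAP 6.2 exception, so an adverse event with onset on the Visit 2 day, known to precede the first combination dose, would be tabulated as emergent on the combination.

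The direction is overstatement of combination TEAEs; no harm is hidden and efficacy is untouched. The size cannot be computed from the documents.

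The conclusion assumes that the first combination dose is taken on the Visit 2 day, as SAP 6.1 has it, and that the programmer follows the row as written. The documents do not say whether the adverse event form records start time or order relative to dose. If it records neither, the SAP 6.2 exception cannot operate in practice.

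**What to change.** In the known-date row of Appendix 2, add a condition for a start date equal to the date of the first combination dose:

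- An event with a start time known to precede the dose, or documented as found in the pre-dose Visit 2 assessments, is not a TEAE. The existing worsening clause of SAP 18.1 still applies if it becomes more severe after the dose.
- A same-day event with onset after the dose, or of unknown order, remains a TEAE under the worst-case rule.

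Refer SAP 6.2 and 18.1 to this rule so that only one operates. Before database lock, confirm what the adverse event form holds. If it has neither start time nor order relative to dose, list Day 1 events separately so that a reader can judge them.

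The cost is a few lines of SAP text and a small programming flag. The combination TEAE count may be slightly lower than under the present row.
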